#### **6.8.1.5 Adverse Event Recording and Reporting**

At a minimum, for patients in either the DP or BSC arm, the investigator must record all AEs and SAEs that occur from the time written informed consent is obtained until Day +60 post-HSCT (or screen failure), regardless of their relationship to study drug or procedure.

Even if the minimum of Day +60 post-HSCT is met, the investigator must continue to record all AEs and SAEs that occur within 30 days after the last dose of defibrotide, regardless of their relationship to study drug or procedure.

For patients who do not receive HSCT, AEs must be collected for 70 days after baseline or early termination, whichever occurs first. For patients randomized but not treated, AEs will be collected for 70 days after randomization or early termination, whichever occurs first.

Any SAE assessed as related to defibrotide or study procedures by the investigator, regardless of time after study termination, must also be recorded.

SAEs must be reported to the Sponsor or its designee using the SAE Reporting Form within 24 hours of first knowledge of the event by study site personnel. Serious adverse event Reporting Forms and contact information will be provided to the study sites separately.

The SAE Reporting Form must be completed as thoroughly as possible before transmittal to the contact provided on the form. The investigator must provide his/her assessment of causality to the study drug and the study procedure at the time of the initial report. If the investigator does not provide a causality assessment of the SAE at the time of the initial report, the event by default will be presumed to be “related”. Follow-up SAE information must be provided to the Sponsor if there are any updates to SAE information previously provided.

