#### 7.4.2.4 Day +100 Post-Hematopoietic Stem Cell Transplant

The following procedures and assessments are to be performed or information will be collected at Day +100 post-HSCT (-7 to 0 days):

- Physical examination, including assessments of the skin, head, eyes, ears, nose, throat, neck, thyroid, lungs, heart, abdomen (with palpation of the liver; and with measurement of abdominal girth for pediatric patients only), lymph nodes, extremities, and a general assessment (including edema). Whenever possible, assessment of right upper quadrant pain will be performed.
- Weight
- Vital signs (blood pressure, pulse, respiratory rate, and body temperature)
- Karnofsky PS ( $\geq 16$  years of age)
- Lansky PS ( $< 16$  years of age)
- EQ-5D-5L (adults only)
- EQ-5D-Y (pediatric patients and parents [proxy version 1])
- Clinical laboratory tests (serum chemistry, hematology, and coagulation)
- Calculation of CrCl (using Cockcroft-Gault for adults and Schwartz formula for pediatric patients). If cystatin C is measured, GFR will be calculated using either the Grubb or Larsson formula.
- Neutrophil and platelet engraftment/graft failure (see [Section 6.8.6](#))
- Abdominal ultrasound (to assess liver and ascites)
- Acute GvHD (i.e., rash, total bilirubin, stool output)
- Chronic GvHD (i.e., rash, mouth, eyes, gastrointestinal tract, liver function tests, lungs, joints and fascia, genital tract, and other symptoms, as clinically indicated)
- Relapse of malignant disease
- Monitoring for VOD-associated MOD (i.e., serum creatinine/CrCl or GFR [optional]/dialysis and supplemental oxygen/ventilator support)
- Resolution of VOD (i.e., bilirubin, ascites, weight, supplemental oxygen/ventilator support, creatinine)
- Immunogenicity sample (see [Section 6.7.1](#))

Defibrotide (JZP-381)  
Clinical Trial Protocol: 15-007 Version 4.0

Jazz Pharmaceuticals, Inc.  
20 August 2018

- Hospitalization information (i.e., dates of hospitalization, dates in ICU, dates of readmission) and inpatient resource use
- Administration of defibrotide (if applicable)
- Monitoring of SAEs considered related to study drug
- Survival status

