## Appendix 2 Schedule of Procedures and Assessments for Patients who Develop VOD and Receive Rescue Defibrotide

Evaluation	Treatment Period				Follow-Up Period From Hospital Discharge Through Completion a		Post-HSCT Assessments (Performed During Treatment or Follow-Up Period) a		
	Diagnosis of VOD Through Hospital Discharge		After First Dose of Defibrotide	Through resolution of VOD b		30 days after last dose of defibrotide c	Day +30 post-HSCT	Day +100 post-HSCT c	Day +180 post-HSCT/ Study Completion or Early Termination
	At VOD Diagnosis	Daily		Other time points	Twice weekly				
Window (days)	NA	NA	±1	NA	±1	+7	-2 to 0 d	-7 to 0	±30
creatinine/CrCl/GFR [optional]/dialysis and supplemental O 2 /ventilator support)									
Resolution of VOD (i.e., bilirubin, ascites, weight, supplemental oxygen/ventilator support, creatinine)			Twice weekly		X	X	X	X	X
PK samples e				Days 1, 7					
Biomarker blood samples (patients weighing >15 kg)	X		X m	Days 7, 14					X
Immunogenicity samples n				Days 14 o , 30 o			X	X	X
Hospitalization data p		X			X	X	X	X	X
Defibrotide administration		X					X (if applicable)	X (if applicable)	X (if applicable)
Concomitant medications q		X					X		
Adverse event assessment		X			X	X	X	X r	X r
Survival status		X			X	X	X	X	X

a. The Day +30 post-HSCT, Day +100 post-HSCT, and Day +180 post-HSCT follow-up assessments should be performed whether the treatment-phase patient is hospitalized or not, or whether the patient's VOD has resolved or not

b. Patients who are discharged from the hospital before resolution of VOD will be monitored twice weekly until resolution of VOD.

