- p. Hospitalization data includes dates of hospitalization, dates in ICU, dates of readmissions, and inpatient resource use (i.e., number of blood product transfusions, amount of coagulation factors administered, frequency and duration of ventilator use and dialysis, number of liver biopsies, ultrasounds, chest images, head images, bone marrow biopsies, abdominal or thoracic drains placed, abdominal or pelvic CT scans, and use of concomitant medications).
- q. Concomitant medications will be recorded up to Day +60 post-HSCT.
- r. Only SAEs considered by the investigator to be possibly related to study drug should be reported more than 30 days after the last dose of study drug.  
ADA=antidrug antibodies; ALT=alanine aminotransferase; ANG2=angiopoietin 2; aPTT=activated partial thromboplastin time; AST=aspartate aminotransferase; BSC=best supportive care; BUN=blood urea nitrogen; CrCl=creatinine clearance; CRP=C-reactive protein; CT=computed tomography; EQ-5D-5L=5-Level EuroQol-5D health questionnaire; EQ-5D-Y=EuroQol-5D health questionnaire for Youth; GvHD=graft-versus host disease; GFR=glomerular filtration rate; HSCT=hematopoietic stem cell transplant; ICU=intensive care unit; IN1RL1=interleukin-1 receptor-like-1; INR=International Normalized Ratio; IWRS=interactive web response system; MCV=mean corpuscular volume; MOD=multi-organ dysfunction; NA=not applicable; PAI-1=plasminogen activator inhibitor 1; PK=pharmacokinetic; PS=performance scale; REG3 $\alpha$ =regenerating islet-derived 3-alpha; SAE=serious adverse event; TNFRI= tumor necrosis factor receptor 1; VACMI=vascular cell adhesion molecule 1; VOD=hepatic veno-occlusive disease; vWF=von Willebrand factor; WBC=white blood cell.

Defibrotide (JZP-381)  
Clinical Trial Protocol: 15-007 Version 4.0

Jazz Pharmaceuticals, Inc.  
20 August 2018

---

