11.2 Adverse Events

Adverse events recorded in the case report form will be coded to SOC and PT using the MedDRA 19.1. The investigator will assess the relatedness of each AE to study drug. The severity of AEs will be recorded using the Common Terminology Criteria for Adverse Events (CTCAE 4.03).

At a minimum, for subjects in either the DP or BSC arm, the investigator must record all AEs and SAEs that occur from the time written informed consent is obtained until screen failure if applicable, or Day +60 post-HSCT, regardless of their relationship to study drug or procedure. Even if the minimum of Day +60 post-HSCT is met, the investigator must continue to record all AEs and SAEs that occur within 30 days after the last dose of defibrotide, regardless of their relationship to study drug or procedure. For subjects who do not receive HSCT, AEs must be collected for 70 days after Baseline or early termination, whichever occurs first. For subjects randomized but not treated, AEs will be collected for 70 days after randomization or early termination, whichever is earlier. Any SAE assessed as related to defibrotide or study procedures by the investigator should be reported regardless of time after study termination. Related SAEs reported after study termination will be collected in the Safety database only.

A treatment-emergent adverse event (TEAE) is defined as any event with onset date on or after the first dose of study treatment (either DP or conditioning regimen) or any ongoing event that worsens in severity after the date of the first dose of study treatment through the protocol-specific reporting period. Only TEAEs with the onset date on or before the end of the protocol-specific AE reporting period noted above will be included in summary tables unless otherwise specified. All AEs will be listed. For the purpose of calculating treatment emergence, incomplete onset dates will be imputed as detailed in Section [8.1.2.1](#).

AEs are graded by the investigator as Grade 1 (mild), Grade 2 (moderate), Grade 3 (severe), Grade 4 (life threatening), or Grade 5 (fatal). The severity grade of events for which the investigator did not record severity will be categorized as “missing” for tabular summaries and data listings, and will be considered the least severe for the purposes of sorting for data presentation.

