Treatment-related AEs are those for which the investigator answers “Yes” to the question “Was this adverse event related to study treatment?” in the eCRF. Events for which the investigator did not record relationship to study treatment will be considered related to study treatment in summaries if the subject received defibrotide. They will be considered not related if the subject did not receive defibrotide. Data listings will show treatment relationship as missing.

Serious AEs are those for which the investigator answers “Yes” to the question “Was the adverse event serious?” in the eCRF. The clinical database will be reconciled with the serious AE database before database finalization.

For all AE summaries, if a subject has more than 1 AE within a PT, the subject is counted only once at the maximum severity and with the closest relationship to study drug. If a subject has more than 1 AE within a SOC, the subject is similarly counted once when reporting results for that SOC. SOC and PT will be sorted by frequency in the DP arm and then alphabetically for those with the same frequency.

The following summaries will be provided (all summaries except the overall summary will be presented by SOC and PT within SOC):

- Overall summary of TEAE

- Summary of TEAE by SOC and PT
- Summary of TEAE by PT
- Summary of TEAE by age group
- Summary of serious TEAE
- Summary of treatment-related TEAE
- Summary of serious treatment-related TEAE
- Summary of Grade 3 or 4 TEAE
- Summary of treatment-related Grade 3 or 4 TEAE
- Summary of TEAE leading to study drug discontinuation
- Summary of treatment-related TEAE leading to study drug discontinuation
- Summary of TEAE by maximum toxicity grade
- Summary of treatment-related TEAE by maximum toxicity grade
- Summary of TEAE leading to death
- Summary of treatment-related TEAE leading to death
- Summary of TEAE by SOC and PT including events recorded outside of the protocol-specific AE reporting period
 - Some sites continued to record AEs beyond the protocol-defined reporting period. This table will summarize all AEs with onset date on or after the first dose of study treatment (either DP or conditioning regimen) through the end of the study.

Additionally, the following TEAE summaries for public disclosure will be provided:

- Summary of treatment-emergent serious AEs (for public disclosure)
- Summary of treatment-emergent non-serious AEs occurring in greater than 5% of subjects (for public disclosure)

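### For rescued patients, Appendix 2 footnote r and Section 7.4.2.4 lack the Day +60 floor on adverse event recording that Section 6.8.1.5 and SAP 11.2 require, so some required safety data may go uncollected

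*Protocol*

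**What the plan says.** **General rule.** Protocol Section 6.8.1.5 states that in either arm "the investigator must record all AEs and SAEs that occur from the time written informed consent is obtained until Day +60 post-HSCT", whatever their relationship to study drug or procedure. It then extends this period, counting from the last defibrotide dose: "Even if the minimum of Day +60 post-HSCT is met, the investigator must continue to record all AEs and SAEs that occur within 30 days". The 30-day limit can therefore lengthen the Day +60 minimum but cannot shorten it. The section also asks for SAEs related to defibrotide or to study procedures without a time limit. SAP Section 11.2 restates the rule and, save for stated exceptions, ties the tables to it: "Only TEAEs with the onset date on or before the end of the protocol-specific AE reporting period noted above will be included in summary tables".

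**Rescue schedule.** In Appendix 2, the row labelled "Adverse event assessment" carries footnote r in its Day +100 and Day +180 cells. The footnote reads: "Only SAEs considered by the investigator to be possibly related to study drug should be reported more than 30 days after the last dose". It does not mention Day +60. The Day +100 visit in Section 7.4.2.4 has a single adverse event item: "Monitoring of SAEs considered related to study drug". That item has no time qualifier, and neither it nor footnote r covers SAEs related to study procedures.

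**Non-rescue schedule.** Appendix 1 footnote x has the same wording as footnote r and also marks only Day +100 and Day +180. Appendix 1 and Section 7.3.1, however, keep weekly adverse event monitoring through Day +60 in both arms, with no footnote restricting it.

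**The concern.** One rule requires an unrelated adverse event on Day +50 to be recorded. Under the other, if the last rescue dose was on Day +15, the same event falls outside what should be reported. A site working from the schedule table could follow footnote r in good faith and stop too early.

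The visit plan does not correct this. A patient diagnosed with VOD moves from Appendix 1 to Appendix 2 and so leaves the weekly Day +31 to Day +60 visits. The first scheduled contact that could pick up a missed event may then be Day +100, where unrelated events are not asked for.

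At stake is the completeness of the Rescue Treatment Phase tables. Protocol Section 9.14.1 summarises adverse events as numbers and percentages of patients, so an event that was never collected counts as no event. The SAP tables would present a period to Day +60 that the rescue schedule does not fully observe.

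**Working it through.** The plan states no figure to reproduce. The check compares dates and then traces the visits.

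**Inputs**
- L: day post-HSCT of the last rescue dose. The documents give no distribution of L, so the values below are illustrative.
- Required end of recording (Section 6.8.1.5, SAP 11.2): the later of Day +60 and L + 30.
- End under footnote r: L + 30.
- Post-dose visit (Section 7.4.2.2): 30 days after the last dose, window +7. It collects all adverse events and its cell has no footnote.
- Next fixed visit: Day +100, window −7 to 0 (Section 7.4.2.4), related SAEs only.

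**Formulas**
- Days required by one rule and excluded by the other: max(60, L + 30) − (L + 30) = max(0, 30 − L).
- Days up to Day +60 left after the latest permitted post-dose visit: max(0, 60 − (L + 37)) = max(0, 23 − L).

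| Last dose (L) | Footnote r ends | Section 6.8.1.5 ends | Days in conflict | Days left if the visit uses its full +7 |
|---|---|---|---|---|
| +10 | +40 | +60 | 20 | 13 |
| +15 | +45 | +60 | 15 | 8 |
| +20 | +50 | +60 | 10 | 3 |
| +22 | +52 | +60 | 8 | 1 |
| +25 | +55 | +60 | 5 | 0 |
| +29 | +59 | +60 | 1 | 0 |
| +30 | +60 | +60 | 0 | 0 |
| +45 | +75 | +75 | 0 | 0 |

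The two rules conflict only when the last dose is before Day +30.

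**Can L be below 30?** Section 1.4 says VOD is typically diagnosed within 21 days of transplant. Section 5.2.1.2 ends rescue at VOD resolution or hospital discharge, whichever comes first. A last dose before Day +30 is therefore possible, but nothing in the documents says how common it is.

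**Which rescued patients have no contact in the gap?**
- In hospital: adverse events are monitored daily (Section 7.4.1.2), so there is no gap in contact.
- Discharged with VOD unresolved: monitored twice weekly until resolution (Section 7.4.2.1), so no gap while VOD persists.
- Discharged with VOD resolved: apart from a Day +30 visit where one falls due (Section 7.4.2.3), the remaining adverse event contacts are the post-dose visit and then Day +100.

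The practical gap therefore needs three things together: an early last dose, VOD resolution and discharge.

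**After correction.** If the footnote used the later of Day +60 and L + 30, the days in conflict would be zero for every L.

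**The case against.** The strongest reply is that Section 6.8.1.5 is explicit, is worded as a minimum and binds investigators whatever a table footnote says. Section 6.8.1.1 also requires every adverse event to be recorded, however it comes to light, and the SAP uses the Section 6.8.1.5 period. This stands in part. The data may be lost, but the documents do not show that they will be. It does not remove the conflict, because the rescue schedule has no visit that carries out the Day +60 rule for the discharged, resolved patient.

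A second reply is that footnote r sits only on the Day +100 and Day +180 cells, both after Day +60. That is true. But its cut-off runs from the last dose, and Day +100 is the next fixed contact after the post-dose visit for these patients. An event from the gap would first be sought there, and both the footnote and Section 7.4.2.4 exclude it unless it is a related SAE.

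A third reply is that the group is narrow and the +7 window shortens the gap. Both points stand and are built into the figures above.

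A reader might also infer more than the documents support:
- *Footnote x shortens follow-up in the defibrotide arm and makes defibrotide look safer.* Appendix 1 and Section 7.3.1 keep unrestricted weekly checks to Day +60 in both arms, so the schedule does not shorten follow-up there.
- *If rescue is more frequent under BSC, the arm comparison is biased.* Footnote r applies equally to rescued patients from both arms, and SAP 8.3 summarises safety by phase and prophylaxis treatment. Bias would need the timing of last doses, or adherence to the footnote, to differ by arm. The documents show neither.
- *Sites stopped recording early.* The SAP says the reverse: "Some sites continued to record AEs beyond the protocol-defined reporting period". It adds a table that includes those events.

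**Conclusion.** The point holds as an internal conflict with a limited practical consequence. Footnote r and Section 7.4.2.4 are narrower than the recording rule in Section 6.8.1.5 and SAP 11.2. For a rescued patient with a last dose on Day L before Day +30, discharged with VOD resolved, up to 30 − L days of required recording may be missed, or max(0, 23 − L) days if the post-dose visit is held at the end of its window.

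This assumes that the site follows the schedule and its footnote rather than Section 6.8.1.5, and that no unscheduled contact reveals the event. The number of such patients, and the direction and size of any effect on the arm comparison, cannot be determined from the documents. Deaths remain known through survival status at each visit. The primary and key secondary analyses, sample size and type I error are unaffected. The conflict is still worth correcting because it concerns safety data in treated patients and is cheap to remove.

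**What to change.** 1. Reword Appendix 2 footnote r, and Appendix 1 footnote x for consistency, along these lines: *After the later of Day +60 post-HSCT and 30 days after the last defibrotide dose, report only SAEs assessed as related to study drug or a study procedure.* Naming procedures brings the footnotes into line with Section 6.8.1.5.
2. Apply the same condition to the Day +100 adverse event item in Section 7.4.2.4.
3. Add one adverse event check at Day +60 to Appendix 2 and Section 7.4.2 for rescued patients, by telephone or at a visit already taking place. A patient still monitored in hospital or twice weekly at that date, or whose post-dose visit falls on or after Day +60, needs no extra contact.

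The cost is the wording changes and one short contact per affected patient. No treatment rule, efficacy analysis or SAP reporting window changes.

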## Appendix 3 Diagnosis of Veno-Occlusive Disease by Liver Biopsy

### Introduction

Confirmation of the clinical diagnosis of veno-occlusive disease (VOD) relies on histological findings including occlusion of terminal hepatic venules and sublobular veins (Shulman et al. 1980), sinusoidal fibrosis (Jones et al. 1987), and hepatic necrosis (Shulman et al. 1980). Using necropsy data in a prospective study of 255 bone marrow transplant (BMT) recipients between 1978 and 1980, McDonald et al. found the positive predictive value of a “certain” clinical diagnosis of VOD to be 88% compared with histological confirmation of venular occlusion in the cohort of 64 patients upon autopsy (1984). Similar results were obtained from an analysis of 235 BMT recipients at Johns Hopkins in whom a cohort of 48 autopsies was evaluable for VOD (Jones et al. 1987). The positive predictive value for a certain clinical diagnosis of VOD was 95%. Of note, the negative predictive value for a certain clinical diagnosis of “no VOD” was 96% and 93% in these 2 series, respectively.

Although the expectation is that the clinical diagnosis of VOD will be the primary information provided to the Endpoint Adjudication Committee (EPAC), it is possible that liver biopsy data will be presented in a subset of patients. This appendix provides a standardized protocol for tissue preparation and analysis of key histopathological VOD features.

### Tissue Preparation

Representative liver tissue will be fixed in formalin per local procedures. From each block, serial 4- to 6- $\mu$ m sections will be cut and stained with hematoxylin and eosin, Gomori’s trichrome or Wilder’s reticulin stain. Sections from a formalin-fixed liver block from each case are stained with an antibody directed against  $\alpha$ 1-antitrypsin (Dako, Carpinteria, CA) and stained by means of an avidin-biotin peroxidase technique so to enhance features of nodular regenerative hyperplasia or nodular transformation (Nakhleh et al. 1988; Wanless 1990)

### Histological Analysis

The following histological features should be examined and provided in a report (to be sent to the EPAC):

1. Hepatic venules
  - a. Occluded hepatic venules Yes/No (defined as concentric subendothelial narrowing of the internal diameter of terminal hepatic and small sublobular venules; use trichrome-stained and reticulin-stained sections)
  - b. Occluded hepatic venules high grade Yes/No (“high grade” is defined as an average percentage of luminal narrowing >33%)
  - c. Venules with eccentric luminal narrowing Yes/No (defined as localized (nonconcentric) widening of the subendothelial zone within hepatic venules and small sublobular veins)

Defibrotide (JZP-381)  
Clinical Trial Protocol: 15-007 Version 4.0

Jazz Pharmaceuticals, Inc.  
20 August 2018

- 
- d. Venules with phlebosclerosis (defined as specimens with fibrotic and unusual concentric thickening of the adventitial layer of the venule wall, often blending with sinusoidal fibrosis)
2. Sinusoidal fibrosis
- a. Sinusoidal fibrosis in zone 3, scored 0 to 3 (higher grades of sinusoidal fibrosis are associated with widening of the sinusoids by an obvious increase of connective tissue and some atrophy of intervening hepatocyte cords; the increase in sinusoidal connective tissue should be based on trichrome or reticulin stains)
3. Hepatocytes
- a. Hepatocyte necrosis in zone 3 (scored 0 to 3)
- b. Nodular regenerative hyperplasia Yes/No (this finding is best seen on reticulin staining and on immunostaining for  $\alpha$ 1-antitrypsin, which is expressed in the enlarged regenerating hepatocytes)

In addition, the pathologist should comment on graft-versus-host disease (GvHD) in the differential diagnosis:

- GvHD is defined histologically as degenerative and destructive changes of the small interlobular or marginal bile ducts.
- Changes of GvHD can be accompanied by a mixed chronic inflammatory infiltrate in the portal space, unrest of the hepatocyte cords and variable degrees of hepatocellular cholestasis in zone 3 and proliferation of dilated periportal cholangioles containing inspissated bile.

